convulsions/tremor/shaking, difficulty talking, a blank stare, eyes rolling up, and profuse sweating. If any of these signs are observed, study personnel will stop the research procedure and inquire whether the subject feels okay. If the subject is unresponsive (and therefore likely experiencing a seizure), first-aid will be supplied. The first-aid response consists of making sure the subject is physically safe for the duration of the seizure. This involves moving the subjects out of the rTMS chair and onto the floor lying down on his or her left side. The subject will be kept lying down on his or her left side, while the staff call emergency medical help, via a 911 call. Resources available in the laboratory include a first-aid kit and immediate phone access. A seizure constitutes a reportable adverse event, and will thus be immediately reported to the IRB via the Safety Events Form mechanism.

The most commonly reported side effect of rTMS is headache. This headache is typically of a muscle-tension type. It usually develops during or immediately after the stimulation and may last for minutes to hours following the end of the stimulation. It is typically limited to the day of stimulation, and usually responds promptly to single doses of over-the-counter pain medications. Neck pain or scalp pain may also occur. Both are usually managed easily with over-the-counter analgesics.

As noted in Rossi et al. (2009), Loo and colleagues reported mild and transient changes in auditory threshold in two depressed patients following a 2-4 week rTMS course of rTMS (Loo et al., 2001). Cases of tinnitus have been reported after rTMS treatments. In addition, in a recent study investigating the effects of rTMS on symptoms of depression, a patient experienced moderate to severe tinnitus after an rTMS session in which earplugs were not used. Rossi et al. recommended that hearing protection always should be worn during rTMS application, and that individuals with cochlear implants not receive rTMS. In the current study, earplugs will be worn by all subjects during rTMS procedures. Individuals with cochlear implants will be excluded from participation.

Risks to the unborn children of pregnant women receiving MRI and rTMS are unknown. Pregnant women will be excluded as per IRB policy. Female subjects are tested once with a urine pregnancy test prior to their first MRI session as per IRB-approved BIAC policy. These female subjects agree not to become pregnant while remaining within the subject pool, and to notify the experimenter or subject coordinator if they become pregnant. If sexually active, the subject must agree to use appropriate contraceptive measures for the duration of the study. Medically acceptable contraceptives include: (1) surgical sterilization (such as a tubal ligation or hysterectomy), (2) approved hormonal contraceptives (such as birth control pills, patches, implants or injections), (3) barrier methods (such as a condom or diaphragm) used with a spermicide, or (4) an intrauterine device (IUD). Contraceptive measures such as Plan B (TM), sold for emergency use after unprotected sex, are not acceptable methods for routine use. If the subject has any uncertainty about whether they could be pregnant, another urine pregnancy test will be performed before they can participate in this protocol. The person(s) who will perform the urine pregnancy test will have successfully completed training as directed by the Chair of Obstetric and Gynecology of the Duke University School of Medicine. The urine pregnancy test kits used for this research study will be those commercially available test kit specified by the Chair of Obstetric and Gynecology and in routine use at DUHS.

11. Costs to the Subject:

There is no cost for subjects to participate in this study.

12. Statistical Analysis Plan:

Shared Analytical Procedures

fMRI analyses. fMRI data are inspected for head motion and data quality using custom BIAC software. Multiple regression analyses use FSL (FMRIB's Software Library, www.fmrib.ox.ac.uk/fsl) FEAT tool (FMRI Expert Analysis Tool). Physiological noise is accounted for in our models by using FSL's PNM toolbox, with a model optimized for brainstem signals. Initial multiple regression analyses are conducted on individual runs, and then across runs for individual participants using a fixed-effects analysis. These analyses are combined across participants within each group using random-effects analyses implemented via FSL's FLAME tool. Between-group comparisons are controlled for multiple comparisons using an FDR alpha set to < 0.05 .

EEG analyses. Pre-processing of EEG includes bad channel replacement, temporal filtering, and ICA analyses to remove artifacts. EEG analyses use either repeated-measures ANOVAs or non-parametric methods (Maris and Oostenveld, 2007b, a) to infer amplitude and latency effects on relevant ERP components and/or sources, as described in each study. Coherence analyses are performed to estimate inter-channel connectivity, with planned analyses on cross-hemispheric and anterior-posterior associations. As done in our past studies, (Appelbaum et al., 2006; Appelbaum et al., 2008; Appelbaum et al., 2010; Ales et al., 2012; Appelbaum et al., 2012) depth-weighted minimum norm analyses will be performed using MRI-derived finite element head models calculated for each participant following alignment of electrode positions to the MRI head surface. Head models are based on compartmentalized tissue segmentations that defined contiguous regions for the scalp, outer skull, inner skull, and the cortex. Cortically constrained minimum norm source estimates are determined by a linear optimization of dipole magnitudes with the least total (root mean square) power while lead field normalization is used to compensate for the inherent bias toward superficial sources.

Specific Study Analytical Procedures

Study 1

TMS data: Mixed model ANOVAs with repeated-measures factors of Frequency (1Hz/5Hz/10Hz), and Number of Pulses (3/15/30 pulses), and rTMS (target, sham [vertex] stimulation) will be performed separately on the median RT and accuracy data. Power analysis shows that 30 subjects/group should be sufficient to see a medium sized effect at an alpha of 0.05. In our previous studies using a Working Memory task with active and sham rTMS over multiple sites, letter set sizes, and task phases, groups of 21 (Luber et al., 2007) 15 (Luber et al., 2008) and 26 (Luber et al., 2013) were sufficient to produce significant effects at the 0.05 level.

[figure not shown]
Study 2

DWI fiber tracking. Our DWI tractography methods have been reported (Davis et al., 2009). For a priori tracts connecting the MT cortex, we use TrackVis (trackvis.org) to identify MT and all connecting regions (FEF, IPS). (Kier et al., 2004b, a) FA values are extracted and analyzed using standard statistics.

Functional connectivity. Task-related functional interactions are estimated using the beta-series correlations (Rissman et al., 2004; Daseslaar et al., 2006). Functional matrices are then evaluated for descriptive graph-theoretical properties (e.g., node degree) using the Brain Connectivity Toolbox (<http://www.brain-connectivity-toolbox.net>). This method has been described before by us (Davis et al., 2012) and others (Fornito et al., 2011; Betzel et al., 2014).

E-field Modeling. Study 2 will rely on the creation of anatomically realistic E-field models of transcranial electric and magnetic stimulation (**Fig. 2**). T1- and T2-weighted

MRI scans are acquired with isotropic voxel resolution of 1 mm. DWI data are obtained with resolution of 2 mm.

Modeling: Head regions are extracted from MRI images, then up-sampled, reoriented, corrected for bias field inhomogeneity, filtered with content-preserving anisotropic diffusion filters, and automatically segmented with software (including gray matter, white matter, and CSF using SPM). High resolution triangular surface meshes of the head model (SimNIBS) are used to compute the E-field (Windhoff et al., 2013). A detailed model of the TMS coil is added to the head model (Fig. 2, center). Isotropic tissue conductivities are assigned to the various tissue compartments.(Opitz et al., 2011) Optionally, we can include anisotropic conductivity in the white matter based on the DWI data, although the impact of white matter anisotropy is small for TMS which affects predominantly superficial cortex (Opitz et al., 2011; Lee et al., 2012). The E-field is computed with a harmonic solver in Maxwell using FEA and scaled in post-processing for the specific pulse shape and amplitude (Deng et al., 2011). **Using the models for targeting:** For SCR in the TMS-induced E-field, the TMS coil will be oriented so that the modeled E-field is normal to the sulcal wall nearest to the recording target to achieve strongest neural activation (Janssen et al., 2014, 2015). For TMS during fMRI or EEG, the peak voxel of fMRI task activation (Session 2) will be used as the center of a 3×3 (A-P and L-R) grid for positioning the coil in simulations of the E-field (Fig. 2, right) corresponding to these 9 coil positions and 6 orientations (54 combinations). The simulation E-field maps will be extracted and correlated, voxel-to-voxel, with the fMRI activation to determine an optimal coil orientation and position. The simulation that yields the highest correlation is selected the optimal coil position and orientation.

Study 3

fMRI Analyses: All EEG, fMRI and behavioral analysis approaches described above will be implemented. However, a unique feature of Study 3 is that it will examine multiple brain states (motor task, color task, rest), while Study 1 and 2 focus on the motor task along. We will therefore capture the cross-task similarities using Independent Components Analysis (ICA), which is useful for identifying consistent relationships between disparate datasets.

TMS data: Mixed model ANOVAs with repeated-measures factors of Site (2 scalp locations, target or vertex), and Brain State (color, motion task, or rest) will be performed separately on the median RT and accuracy data.

13. Data & Safety Monitoring:

The subjects will be fully informed of the nature of the study requirements prior to enrollment and periodically throughout the study. The subject's wellbeing will be continuously monitored by the experimenter, and the Principal Investigator will report all

serious adverse events in an expedited manner to the Duke University Health System (DUHS) Institutional Review Board (IRB) office and all applicable regulatory authorities in accordance with the Center's standard operating procedures.

The study monitor will be [name]. [name] will ensure the quality of the study and establish that each co-investigator is complying with the investigational plan and IRB regulations. Monitoring of this protocol is simplified by the fact that this study involves a small number of investigators and a single facility in which the study is being conducted.

Throughout the investigation, the monitor will ensure that the facilities being used continue to be acceptable for the purposes of the study, that the investigational plan is being followed, that any changes to the protocol have received IRB approval and have been reported to the sponsor, that accurate, complete, and current records are maintained, that accurate, complete, and timely reports are made to the IRB. This will be accomplished through quarterly meetings during which the status of the protocol, investigators, and IRB compliance are reviewed. The monitor will review each research chart for completeness and accuracy. He will confirm that inclusion and exclusion criteria have been met for each subject enrolled, and compliance with all other aspects of the investigational plan are met.

14. Privacy, Data Storage & Confidentiality:

Section 12 of the e-IRB submission form have been completed.

Words Cited

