The study procedures outlined below cover 3 integrated experiments. A general overview of each study suggests a highly integrated set of experiments that will help explain neuromodulatory effects. **Study 1** investigates the effects of **frequency** and number of pulses, manipulated across blocks. rTMS is applied to MT or the vertex at 7 doses consisting of up to 30 pulses at 1, 5, or 10Hz. **Study 2** manipulates the **location** and orientation of the coil during rTMS of MT to bias rTMS effects either toward the dorsal pathway or toward the ventral pathway. **Study 3** manipulates **brain state** and uses *motion task blocks*, as in Studies 1 and 2, but also *color task blocks* and *rest blocks*. As in Study 2, only 5Hz rTMS is used. Therefore, we describe first the *shared* design information, and then describe design information *specific* to each of the 3 Studies.

Table 1. TIMELINE OF STUDY PROCEDURES:

Assessment	Screening Session	Session 1 (Shared)	Session 2 or 3 TMS-fMRI	Session 2 or 3 TMS-EEG
1. Subject consent & questionnaires	X			
2. Urine Test	X			
3. Practice with Motion task	X			
4. TMS Tolerability	X			
5. TMS Motion disruption, phosphene and motor thresholds	X			
6. Structural MRI (T1 & DWI)		X		
7. Resting-state fMRI		X		
8. Event-related fMRI with Motion task		X		
9. Concurrent TMS-fMRI with Motion task			X	
10. Concurrent TMS-EEG with Motion task				X
11. Side Effect Checklist	X		X	X

The Table above presents the timeline of major study procedures.

Shared Design Details

Subject Screening. In each of the 3 studies proposed, 48 different healthy young adults (18-30 y.o.) will participate in both TMS-MRI and TMS-EEG components of each study. Participants will have no psychiatric or neurological history and no ongoing psychoactive drug use (for more details see Section 5 below). Normal right-handed volunteers will be recruited from the community.

Each participant will take part in up to **seven** sessions: the first two sessions are *shared* by the TMS-MRI and TMS-EEG components of each study. The third and fourth sessions correspond separately to the TMS-fMRI and TMS-EEG sessions—with designs specific to each of the 3 Experiments—with the order counterbalanced across participants. If participants have been included in the pilot protocol, they will have two additional visits. Finally, an additional visit is built in if subjects need to make up a visit (e.g. poor task performance).

[figure not shown]

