Study 1 investigates the effects of **frequency** and number of pulses, manipulated across blocks. Table 2 describes the 7 conditions used in this experiment. rTMS is applied to MT or the vertex at 7 doses consisting of up to 30 pulses at 1, 5, or 10Hz. In conditions 1–3, these frequencies are delivered for 3 seconds leading to 3, 15, and 30 pulses, respectively. In conditions 4 and 5, frequency remains at 10Hz, but durations are 1.5 and .3 seconds, respectively, to yield

Table 2. Conditions in Study 1

Cond	Sites	Hz	Sec.	Pulses
1	MT	1	3.0	3
2	MT	5	3.0	15
3	MT	10	3.0	30
4	MT	10	1.5	15
5	MT	10	0.3	3
6	Vtx	1	3.0	3
7	Vtx	10	3.0	30

numbers of pulses that match conditions 1 and 2. Thus, we manipulate frequency while keeping duration constant, and number of pulses while keeping frequency constant. In control vertex stimulation conditions 6 and 7, rTMS is delivered for 3 seconds at 1Hz or 10Hz, matching the pulses of conditions 1 and 3, respectively.

Each of the 7 conditions is assigned to two blocks of 20 trials each (40 trials/condition); each trial lasts 10 seconds, and we will administer 14 blocks (47 minutes, 280 trials total) in both the TMS-fMRI and TMS-EEG experiments. The TMS-fMRI and TMS-EEG will necessitate 60 minutes preparation to adjust the positioning for the TMS coil and—in the TMS—EEG experiment—apply the EEG cap, as well as 30 minutes for a brief rTMS side effect rating scale and visual analog mood ratings will be administered before and after each rTMS block. Thus, the entire session will last 3 hours for both the TMS-fMRI and TMS-EEG Session. As above, subjects' side effects will be monitored closely, and all side effect monitoring described above will be repeated. Furthermore, all intensities fall within the rTMS safety guidelines (Rossi et al., 2009b).

Study 2

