- g. Mini Mental Status Exam (MMSE) score of <24.
- h. Parkinson's disease.
- i. Huntington's disease.
- i. Multiple sclerosis.
- 7. Increased risk of seizure for any reason, including prior diagnosis of increased intracranial pressure (such as after large infarctions or trauma), or currently taking medication that lowers the seizure threshold.
- 8. Subjects with cochlear implants
- 9. Subjects not willing to tolerate the confinement associated with being in the MRI scanner.
- 10. Women who are pregnant or breast-feeding (urine test).
- 11. Blindness.
- 12. Inability to read or understand English.

6. Subject Recruitment & Compensation:

We will recruit 264 total subjects into our 3 Studies. Prior to the main experiment for each Study, we will recruit pilot subjects to refine the experimental procedure and ensure adequate power (n=40 for each of 3 Studies, n=120 total). Then, for the main experiments, 48 subjects will be recruited for each study (n=144 total). Thus, 48 volunteers will be recruited for each Study, half male, half female, in order to achieve three groups of 38 completers for each study, given a 20% drop-out rate.

Subject Recruitment: Neurologically normal volunteers will be recruited from either a subject pool maintained at the BIAC for MRI (IRB protocol Pro00010672), [the](#) IBRC SONA site, Duke List (www.dukelist.edu), Craigslist, or flyers distributed on campus locations. Additionally, subjects who have participated in another active TMS Study (Protocol 000065334) and have explicitly indicated a willingness to be contacted for future experiments, may be contacted for participation in the current protocol. Male and female subjects from all racial and minority groups will be accepted.

Subject payment: \$20 per hour, approximately \$300.00 total for screening session (2 hrs), MRI session (2 hrs), and up to 4 additional sessions pairing TMS with another data collection technique (2 hrs each). 15 hours represents the maximum possible participation, including piloting and the full study, with the possibility of making up one visit. Payment will be made by via direct deposit for individuals with a Duke Unique ID or by check sent by mail within a few weeks after the end of their study involvement.

7. Consent Process:

Section 14 questions have been completed on the e-IRB submission form.

8. Subject's Capacity to Give Legally Effective Consent:

N/A: Only involves healthy volunteers

9. Study Interventions:

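### Pilot participants may enter the main experiments, so settings refined in the pilot could be tested partly on the people they were refined on, and no rule or analysis term covers the overlap

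*Combined protocol and SAP*

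**What the plan says.** Section 4 (Shared Design Details, Subject Screening) sets the ceiling: "Each participant will take part in up to seven sessions". It reaches that number by adding two shared sessions, two TMS sessions, a make-up visit and, for some, pilot visits: "If participants have been included in the pilot protocol, they will have two additional visits". Section 6 (Subject payment) confirms that one person may do both: "15 hours represents the maximum possible participation, including piloting and the full study, with the possibility of making up one visit".

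Section 6 gives the purpose of the pilot: "Prior to the main experiment for each Study, we will recruit pilot subjects to refine the experimental procedure and ensure adequate power". The Piloting part of Section 4 adds that it should find the stimulation onset giving participants the greatest gain.

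On numbers, Section 6 states "We will recruit 264 total subjects into our 3 Studies", made up of a pilot ("n=40 for each of 3 Studies, n=120 total") and the main experiments ("48 subjects will be recruited for each study (n=144 total"). The Piloting part of Section 4 instead gives 264 pilot participants, 88 per Study.

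On duration, the descriptions of Studies 1 to 3 each say "Thus, the entire session will last 3 hours for both the TMS-fMRI and TMS-EEG Session". The payment paragraph in Section 6 lists up to four TMS sessions at 2 hours each.

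None of the criteria in Section 5 concerns pilot participation. Section 12 does not mention it.

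**The concern.** If timing or other settings are chosen because they worked well in a set of people, and some of those people supply the main data, the main experiment is not an independent test of those settings. Chance features of the pilot that drove the choice can carry over. A within-subject design does not remove this, because what is tuned is the condition effect itself.

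Two smaller risks follow. Pilot performance and tolerance are known before the main experiment begins, and nothing stops re-invitation from being guided by them. Re-entrants would also bring more task practice, and possibly more rTMS exposure, to a task with fixed 3% and 18% coherence set to give about 60% and 90% correct. If practice changes how a person responds to one rTMS condition relative to another, the average contrast depends on how many re-entrants are in the sample.

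**Working it through.** **1. Sessions.** Inputs: Section 4, Subject Screening. 2 shared + 2 TMS + 2 pilot + 1 make-up = 7, which reproduces the stated maximum. The figure therefore has re-entry built in. Without pilot visits it is 2 + 2 + 1 = 5.

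**2. Headcount.** Inputs: Section 6. Pilot 3 × 40 = 120; main 3 × 48 = 144; 120 + 144 = 264, which reproduces the stated total. With k re-entrants in each Study, distinct people = 264 − 3k, and main participants without pilot exposure = 48 − k per Study.

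| k per Study | Distinct people | Main participants without pilot exposure, per Study |
|---|---|---|
| 0 | 264 | 48 |
| 10 | 234 | 38 |
| 20 | 204 | 28 |
| 40 | 144 | 8 |

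The last row is the arithmetical limit under Section 6's pilot size; nothing in the plan says it is intended. Under the Piloting part of Section 4 (3 × 88 = 264 pilot participants), pilot plus main without overlap would be 264 + 144 = 408. Since 40 + 48 = 88, the Section 4 figure may be the overall total placed under the wrong label, but the document does not say so.

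**3. Hours.** Inputs: screening 2 h and MRI 2 h (Section 6); TMS sessions 2 h (Section 6) or 3 h (Section 4, Studies 1 to 3). Neither the pilot visit nor the make-up visit has its own stated length, so 2 to 3 h is assumed where TMS sessions are 3 h. The stated maximum agrees with the payment: $300 / $20 per hour = 15 h.

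| Session lengths | Main only | Main + make-up | Main + pilot | Main + pilot + make-up |
|---|---|---|---|---|
| All TMS, pilot and make-up visits 2 h | 2+2+2×2 = 8 | 10 | 12 | 14 |
| TMS 3 h, pilot visits 2 h | 2+2+2×3 = 10 | 12–13 | 14 | 16–17 |
| TMS 3 h, pilot visits 3 h | 10 | 12–13 | 16 | 18–19 |

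With the payment section's 2-hour sessions, re-entry plus a make-up fits within 15 h. With the design section's 3-hour sessions it comes to 16–19 h.

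**4. Exposure.** Every participant practises the task for about half an hour during visual cortex stimulation at screening and performs it again in the MRI session (Section 4, Shared Sessions 1 and 2). The Piloting part drops Steps 6–10 of Table 1, and Steps 9 and 10 are the TMS task sessions. It also says that pilot timing matches Studies 1 to 3, which run 280, 240 and 360 trials per session. Extra pilot exposure could thus be anything from a repeat of screening-type practice to full-length rTMS sessions.

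**5. Analysis.** The behavioural models in Section 12 use frequency, number of pulses and stimulation site (Study 1), and site and brain state (Study 3), all repeated-measures factors. There is no factor, exclusion or sensitivity analysis for prior pilot exposure.

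**The case against.** Much can be said for the plan as it stands.

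- **The contrasts are within-subject.** Each person is their own control, so a practised participant's shift in overall RT or accuracy does not bias a comparison of conditions. This stands. Only an exposure-by-condition interaction would matter, and the documents give no basis for its size or sign; practice could shrink an effect or enlarge it.
- **Nobody is naive at the TMS sessions.** Screening and the MRI session give everyone practice, and people from another TMS study may also be recruited. This stands: the difference is one of amount.
- **The scope for tuning may be small.** The shared motion task already fixes when bursts end. The pilot positions the coil by the 10-20 system, whereas the main study uses individual imaging, so spatial targeting is not tuned on pilot participants. The timing aim is also worded in terms of working memory, although the task is motion discrimination. This limits the likely size of the problem. It does not remove the stated purpose in Section 6, which is to refine the procedure.
- **Selective re-invitation is not described anywhere.** Correct; it is a possibility left open.

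A reader might also infer that re-entry by itself breaks the 15-hour maximum. It does not: the payment paragraph allows for piloting and gives 14 h with a make-up. The excess comes from the separate 2-hour versus 3-hour conflict. Likewise, overlap does not exceed the headcount; it turns 264 into an upper limit.

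**Conclusion.** The point holds as a design weakness that should be closed. The plan expressly allows the same person to be in the pilot and the main experiment, uses the pilot to refine what the main experiment tests, and has no cap, exclusion or analysis term for the overlap. What remains at risk is the independence of the main test, possible selective re-invitation, and an exposure-by-condition interaction of unknown size and direction.

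The countable consequence is that distinct people number 264 − 3k, from 264 down to 144 if all 40 pilot participants per Study re-enter. This uses Section 6's pilot size. The documents do not support a figure for lost effect size or power, because they say neither how many would re-enter nor how practice changes the response to rTMS.

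Two inconsistencies are separate and would remain if re-entry were barred: TMS session length (2 h in Section 6, 3 h in Section 4) and pilot size (264 in Section 4, 120 in Section 6).

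**What to change.** Add an exclusion to Section 5: anyone who took part in the pilot of any of the three Studies is not eligible for the main experiments. Make the matching edits together:

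- In Section 4 (Subject Screening), delete the sentence on two extra visits and change the maximum from seven sessions to five.
- In Section 6, delete the reference to piloting from the maximum-participation sentence, and revise the count of up to four TMS sessions and the hour and payment totals. Without pilot visits the maximum is 13 h with 3-hour sessions, or $260 at $20 per hour.

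If re-entry is kept, or has already happened, record pilot exposure for each participant and report the primary contrasts with and without those participants.

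Separately, reconcile the 2-hour and 3-hour session lengths with the 15-hour maximum, state the length of a pilot visit and what it contains, and reconcile the two pilot sizes.

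The cost is protocol wording and the loss of willing pilot volunteers for the main study. On Section 6's figures no extra recruits are needed, since 120 and 144 are already added as separate people. If Section 4's pilot size is the intended one, separate samples would need 408 people, so the pilot size must be settled first. The exclusion would not give a sample free of TMS experience, because recruits from the other TMS study stay eligible; its purpose is to keep the tuning and testing samples apart.
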